## **15.0 Risks to Subjects**

**Inconvenience, Discomfort, and Boredom:** Some participants may experience distress by questions pertaining to their trauma or their emotional functioning. All participants will be informed at the outset that the study is voluntary, and they may terminate participation at any point. Our past and ongoing research suggests that data collection using many of these measures can be conducted without undue psychological distress or exacerbation of symptoms. This experience includes substantial research with younger and older adults, active duty service members, military Veterans, rape victims, victims of other forms of violence (e.g., natural disasters, car accidents), and work on large-scale studies asking questions about similar topics with general population samples. Legal risks arise if individuals are homicidal or suicidal and make these intentions known to project staff, who may then be required to notify authorities and the target of homicidal intent. These risks are outlined in the informed consent documents.

Some participants may experience a temporary increase in PTSD symptoms during the Prolonged Exposure (PE) treatment. This is normal, not unexpected, and not associated with negative treatment outcomes. Research by our group and others shows that the majority of patients undergoing PE treatment do not experience an increase in symptoms, and that any increases in symptoms that do occur are mild-moderate, temporary, and not related to retention or end of treatment PTSD symptoms.

In the event that subjects experience psychological distress secondary to participation, they will be encouraged to contact the Principal Investigators. [name] (PI) is a licensed clinical psychologist and Staff Psychologist at the VA. Participants will be given contact information for [name] at the time of consent, as well as resources for local and national 24-hour hotline numbers. In addition, participants will have access to urgent care services at MUSC and the VA. The research team is comprised of licensed clinical psychologists with extensive experience working with adults who have experienced significant life stressors and PTSD. If assessors or project staff believe that a participant is significantly distressed by participation, the PI will be notified and will contact the participant immediately to assess distress and assure participant safety. If called by a participant, the PI will attempt to address all participant concerns and will set up an alternate referral for clinical services outside the project if desired.

**Physical Discomfort:** Participants may experience some physical discomfort from wearing the device. The foam electrode gel may cause mild irritation though the electrodes being used have a unique, patented pre-gelled adhesive side with non-irritation gel especially developed to prevent allergic reactions. The foam electrode is latex free and therefore suitable for every skin type. We will instruct participants how to appropriately wear the device and have them practice wearing it. We will also provide written and illustrated instructions for how to wear and use the device during in vivo exercises to ensure it is as comfortable as possible.

**Confidentiality:** All possible efforts to protect participants' privacy and confidentiality will be made throughout the course of the study. Participants will be provided with a written informed consent document which specifies the risks and confidentiality protections and limits of study procedures.

**Sources of Materials:** Data will be in the form of structured clinical interviews, self-reported questionnaires and subjective units of distress scale (SUDS) ratings, and physiological data that will be obtained specifically for research purposes. Access to research records will be limited, as they will be maintained in a locked cabinet in the project coordinator's locked office within MUSC or VA. Only researchers working

on this project will have access to the participants' data. The material will be specifically obtained for research purposes. Telehealth sessions will be conducted using only approved MUSC/VA applications to maintain confidentiality. Data will be collected by trained study personnel under the direct supervision of [name] (PI). Participants will be permitted all the time they need to ask questions and/or consult with family members. Participant will be fully informed of all aspects of the study before signing the informed consent and beginning any study procedures.

### **Adequacy of Protection against Risks**

**Recruitment and Informed Consent Procedures:** Participants will be primarily recruited from the Ralph H. Johnson VA Medical Center (VAMC) and the Medical University of South Carolina (MUSC). IRB-approved flyers and brochures describing the study and providing contact information will be placed in the PTSD and mental health clinics at both hospitals. We will also post IRB-approved recruitment flyers in prominent locations in other VA and MUSC hospital clinics (e.g., internal medicine, women's health, emergency department). We will additionally recruit from the general community via online and local media advertisements. The research team has used these methods successfully in previous and ongoing research studies to recruit veterans and civilians with PTSD and other psychiatric conditions.

The research team and all of the study staff have completed (or will complete upon hiring) the Miami Collaborative IRB Training Initiative (CITI) course and its associated tests in research ethics. Informed consent (IC) will be collected at the study research offices, in a private, interruption-free environment. The PIs, Co-Is, or a Study Coordinator will obtain IC. The IC form will outline: a) the sponsorship of the study; b) the nature, purpose and procedures of the study; c) the voluntary nature of participation (i.e., participation is not required; participation can be discontinued at any time); d) the duration of the study; e) potential risks and discomforts, as well as benefits of participation; f) that all information will be kept confidential subject to the provisions of the state and federal law; g) compensation; and h) alternative treatments. The IC form will specifically review the potential for psychological distress, and the risks associated with treatment that may occur as a result of study participation. The IC form will be explained to participants in easy-to-understand language, and participants will be instructed to read the form carefully prior to signing it. The IC form will include emergency contact information for the PIs. Any questions pertaining to the study or consent process will be answered fully. Potential participants will not be required to make a decision to participate at the initial contact, though that possibility will be available. If participants wish to discuss study participation with their family and/or significant others, they will be encouraged to do so. Participants will be informed that they can discontinue their participation in the study at any time and that this decision will not influence the care they receive at MUSC or the VAMC. Consent will be documented by the signature of the participant on the IC form, accompanied by the signature of the individual obtaining the consent. Participants will be given a copy of the informed consent to keep. Research staff will document the informed consent process in the medical record of the participant.

**Confidentiality:** Risks to confidentiality will be minimized by using initials and code identifiers. There will be no linkage between a participant's identity and their responses. There will be only one master list of participants (not linked to any participant responses) which will be kept locked separate from all data and will be available only to the PI, Co-Is and approved study personnel. All data will be stored in a confidential manner (i.e., in locked files or on encrypted computers in the Study Coordinator's office) so as to protect the confidentiality of participant information. Access to research records (paper and computerized) will be restricted to the project staff. Our research staff are well trained in the confidential nature of research subjects' records. Research staff complete annual courses on confidentiality protection and most recently on HIPAA regulations. These procedures are highly effective in protecting confidentiality issues. Names will not be used on specimens, assessments or be available in the research laboratory. The investigators and all study personnel will sign a confidentiality agreement that no identifying information of specific individuals will appear in any internal reports or external documents (e.g., peer-reviewed publications, presentations). Participants' data will be entered in a computer database with only number codes for

identifiers and will not identify study subjects by name or other identifiers (e.g., birth date). These procedures have proved highly effective in preventing breaches of confidentiality in our current and previous research studies.

**Assessment Procedures:** Risks associated with assessment and treatment include the possibility that participants might be upset by questions pertaining to trauma or their emotional functioning or talking about their trauma. The research team will closely monitor participants for any increase in distress at every treatment visit. PTSD and depression symptoms will be monitored weekly using standardized measures (PCL-5, BDI-II) in order to detect any symptom worsening requiring further evaluation. Additionally, participants will be advised to observe any signs of worsening PTSD, depression, and other symptoms, and to discuss these with the research team. All participants will be informed at the outset that they may terminate participation at any point. If a participant becomes upset in-between visits, he or she will be encouraged to contact the Study Coordinator, their Study Therapist, and/or [name]. If a participant needs or desires immediate attention, arrangements will be made for an appointment with an experienced mental health provider. The informed consent document provides direction to contact the study staff during office hours and/or the Emergency Room at any time for worsening of symptoms.

Our previous and ongoing PTSD research suggests that data collection using many of these measures can be conducted without undue psychological distress or exacerbation of symptoms among participants. This experience includes substantial research with younger and older adults, military service members, rape victims, victims of other forms of violence, and work on large-scale studies asking questions about similar topics with general population samples. In addition, it includes Veterans with military-related PTSD. In the event that participants experience extreme psychological distress secondary to participation, they will be encouraged to telephone the PIs. In addition, they will have access to urgent care services at MUSC and the Ralph H. Johnson VAMC. The research team is comprised of licensed clinical psychologists with extensive experience working with adults who have experienced significant life stressors and addiction. If project staff believes that a participant is significantly distressed by participation, [name] will be notified and will contact the participant immediately to assess distress and assure participant safety. If called by a participant, [name] will attempt to address all participant concerns and will set up an alternate referral for counseling for those who desire it from outside the project. All participants will review, at the initiation of participation, an informed consent document which specifically reviews potential psychological distress from the assessments or PE therapy as a potential outcome of participation. If necessary, they will be asked to complete a safety plan and agree to call the project staff or 911. However, if safety is in question in the minds of any project staff, the Mobile Crisis unit of Charleston County, which involves a team of police and psychiatric workers, or the EMS unit will be dispatched to the participant's home to assure safety. In our NIH-, VA- and DoD-funded clinical trials of PTSD treatment provision, we have not had any problems related to participation that could not be safely resolved with these methods.

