inconspicuous. The *clinician interface* will include a “dashboard” or display (see **Figure 2**) to enable live video of the patient’s environment; real-time streaming of heart rate (HR) and galvanic skin response (GSR); SUDS ratings; and a secure system to store and review completed IVEs offline. New capability will be designed to allow clinicians to demarcate moments of interest during IVEs (e.g., with a time stamp or event marker) which may be “hot spots” (similar to hot spots in imaginal exposures) when the patient’s physiological and/or subjective levels are high; those will be stored and can be replayed and/or reviewed in the future to help instruct patients on what to do (or not do) in subsequent IVEs to optimize engagement and efficiency. The dashboard will include summary statistics for each IVE, such as the total number of minutes spent in the exercise, as well as mean and peak HR, GSR, and SUDS ratings. The *cloud-based system* is HIPAA-compliant and designed to rapidly store quantitative and qualitative data from IVEs. Summary reports for individual patient in vivo assignments will be stored and allow for comparisons across multiple IVEs within each person and across treatment conditions. These reports will access data from the session database as well as the system usage logs. The database will be secure and backed up daily.

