## **7.0 Setting**

All procedures will be conducted on the MUSC campus or at the Ralph H. Johnson VA Medical Center (RHJVAMC). Subjects recruited through VA will complete research procedures at the VA or through VA-approved telehealth interface (consent, baseline appointment, weekly assessments, prolonged exposure therapy). VA subjects will be consented via telehealth only if and when consent via telehealth is approved at VA. Subjects recruited through outside of the VA - or subjects who are not receiving care at the VA will complete research procedures at MUSC or through telehealth (consent, baseline appointment, weekly assessments, prolonged exposure therapy). Out-of-office IVE locations will vary based on subject's needs and will take place at the designated location decided on by the subject and study team. No research procedures will take place at Zeriscope.

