**Prolonged Exposure (PE) Therapy.** PE will be delivered based on Foa's therapy manual (Foa et al., 2019). Specific to this study, participants will be asked to wear the apparatus during therapy sessions. During session 1, the Study Therapist will provide the rationale for PE, review trauma history, conduct breathing retraining, and orient the patient to the apparatus. Session 2 will include review of common reactions to trauma, introduction of SUDS, in vivo hierarchy development, instructions on how to use the IB-PE system, and a brief in-session practice. During the in vivo hierarchy development, participants will work with the study therapist to identify stressful triggers, listing these from most stressful to least stressful. The most stressful situation will be listed at the top of the hierarchy. A large part of PE therapy is safely exposing the participant to these individualized stressful situations (for example, going to a mall, walking in a crowded grocery store, visiting a park or engaging in a stressful activity, such as watching a suspenseful video clip). Part of the PE therapy includes going to these stressful situations as "homework" each week. That is, participants will be asked to expose themselves to their identified stressful scenarios outside of the office. Specific to this study, participants will be asked to wear the apparatus during these exercises. The exercises will be audio and video recorded. Sessions 3-9 include in vivo "homework" review

and planning for next in vivo assignments, imaginal exposure, and processing. During session 10, the therapist and patient review treatment progress and discuss potential next steps depending on each patient's needs (e.g., couple's therapy, vocational counseling). A participant may be offered the option of two additional sessions of PE (for a total of 12 sessions) if he or she does not demonstrate sufficient improvement of PTSD symptoms as determined by a decrease of 10+ points in PCL-5 score from Baseline to Session 9. All Study Therapists will have a master's or doctoral degree, complete a PE training, and attend weekly supervision during the trial. Sessions checklists will be used for fidelity to the manual (Carroll et al., 2007).

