As shown in **Figure 3**, 10 sessions of PE will be delivered, with the possibility for participants to complete two sessions per week. Prior to using the IB-PE system, participants will use the system to develop an 'in-office' baseline that will be used for reference throughout the IVEs. Another 'in-office' baseline will be recorded at final session to assess physiological and subjective changes that have occurred throughout the course of the treatment. All participants will wear the IB-PE system, affording maximum data collection during IVEs and thorough evaluation of the new system. The in vivo exercises will be guided by either the Study Therapist or a clinical support team member. This role will be referred to as the 'IVE Coach.' The participants will be randomly assigned to either IB-PE (guided) or to IB-PE (record only) based on a 3 to 1 randomization scheme (3 guided: 1 record only). In the guided group, the IVE Coach will lead the participant in the in vivo exercises. The IVE Coach will use actionable data during IVEs (e.g., HR, GSR) to modify the assignments in real time. The IVE Coach will virtually accompany patients to at least three IVEs. After that the IVE Coach will start out the session by guiding the participant for the first several minutes, then will leave the session once the participant demonstrates competency in finishing the exercise on his or her own. The IVE Coach will be in close communication with the rest of the clinical support team regarding the participant's IVE completion. Study Therapists will receive a system notification each time a patient completes an IVE, along with a summary report from that assignment (e.g., total time,  $\bar{x}$  and peak GSR). These data may be used to objectively monitor treatment progress and discussed with the patient in the office (e.g., to highlight habituation within or between IVEs) (Rauch et al., 2018). In the record-only group, passive data collection will be utilized to collect and store biometric and behavioral data for future offline analyses to investigate predictors of outcome. Wifi availability will be considered in the selection of the therapist-guided locations for IVEs. In the rare event that wifi signal is not present during a therapist-guided IVE, the participant and IVE Coach would work together to find an alternate solution (complete the IVE without wifi, and/or complete an additional therapist-guided IVE at another time and location, and/or reevaluate the in vivo hierarchy and make modifications to include locations with wifi). If equipment malfunctions at any point throughout the study, a replacement system will be provided to the participant. Zeriscope will be notified of equipment malfunctions.

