
**Figure 3. Overview of the randomized clinical trial.** Participants (N=40) randomized to 10 sessions of PE (once or twice weekly visits) and either a) PE with guided IVEs using Intelligent Biometrics (IB-PE Guided) or b) PE alone (IB-PE Non-guided).

How the IVE Coach will guide the patient through IVEs: While there will be some variability based on individual patients and specific in vivo activities, the patient and IVE Coach will use synchronous audio/video to communicate, and will provide a brief (3 min) review of the instructions before the patient begins the IVE. In addition, a baseline for each IVE will be established prior to beginning the IVE exercise. If the patient is optimally engaged in the exercise, as demonstrated by increasing physiological (e.g. skin conductance, heart rate) and subjective (increase in SUDS scores) indices, the IVE Coach will provide

encouragement to continue but will not interrupt the patient. If the patient is not engaged (e.g., showing low/no increase in physiological and subjective indices of engagement, not following instructions, engaging in distraction behaviors), the IVE Coach will intervene and review the instructions, provide specific guidance to help the patient engage, and provide feedback until the patient is optimally engaged to maximize benefits. After the IVE, a brief (5 min) processing will occur. The IVE Coach will ask the patient how he/she thinks the exercise went, what was learned, and plan the next IVE. The IVE Coach will complete a check-out form documenting how the exercise went and will communicate this with the clinical support team.

**Telehealth:** Participants in this research study may choose to complete informed consent/baseline appointment, study visits and therapy sessions via home-based telehealth (HBT) care (i.e., service delivery to patients in their homes using consumer-friendly, video-conferencing technology) which may likely enhance retention by directly circumventing financial and transportation barriers associated with traveling to MUSC/VA for in-person sessions. HBT sessions will be delivered via standard desk, laptop computer, tablet, or smartphone running MUSC/VA approved applications.

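### The emergency rule in Section 15.0 sends responders to the participant's home, which is the wrong destination if the crisis arises during an in vivo exposure elsewhere

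*Combined protocol and SAP*

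**What the plan says.** The rule is in the protocol, Section 15.0, under Adequacy of Protection against Risks, in the text that begins with Assessment Procedures. It provides that "if safety is in question in the minds of any project staff, the Mobile Crisis unit of Charleston County", described there as a team of police and psychiatric workers, "or the EMS unit will be dispatched to the participant's home to assure safety". The trigger is a doubt held by any staff member. The rule is not limited to a type of visit, and the home is the only destination it names.

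The same block opens by referring to risks of both assessment and treatment. Just before the rule, it says that the consent document reviews "potential psychological distress from the assessments or PE therapy as a potential outcome of participation".

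Section 10.0 makes exposure outside the office part of that therapy: "Part of the PE therapy includes going to these stressful situations". Section 7.0 says that out-of-office "IVE locations will vary based on subject's needs and will take place at the designated location decided on by the subject and study team". In the guided arm, Section 10.0 adds that "The IVE Coach will virtually accompany patients to at least three IVEs". This contact is by live audio and video.

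**The concern.** The home is a natural destination for someone who telephones in distress or who is on a home telehealth visit. It does not suit the feature that sets this trial apart, which is staff following a participant remotely, in real time, at a place chosen because it provokes distress. A coach who sees a crisis in a store and applies the rule as written sends responders to an address where the coach knows the participant is not.

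What is at stake is the delay before help reaches the participant. Any staff member may have to use a dispatch rule under time pressure, so it should be correct without interpretation. No endpoint, comparison or analysis is affected.

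**Working it through.** No arithmetic applies. The plan gives no figure on this point, and the documents give no emergency rate from which one could be built. The check sets the emergency text beside the text on where exposures happen and how staff follow them.

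1. **Does the rule reach IVEs?** On its wording, yes. The trigger is general, the block's opening covers treatment, the consent sentence names PE therapy, and Section 10.0 makes out-of-office exposure part of PE. The block does not mention IVEs, however. Its heading is Assessment Procedures, and the steps leading up to the rule are mostly made by telephone: the participant calls the investigators, the principal investigator contacts the participant, and a safety plan is agreed if needed. It was probably written mainly with telephone welfare checks in mind.

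2. **Where is the participant during an IVE?** Section 7.0 says that sites vary and are agreed with the study team. The examples in Section 10.0 include a mall, a crowded grocery store and a park. Another example, watching a suspenseful video clip, could be done at home.

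3. **How would staff learn of a crisis there?** In the guided arm, through live audio and video (Section 10.0) and the clinician dashboard (Section 3.0). The coach is present only virtually. In the record-only arm the data are collected passively for later analysis, so staff would learn mainly from a call by the participant or from contact by the principal investigator (Section 15.0).

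4. **Apply the rule to each setting.**
   - Telehealth visit at home: the home is correct.
   - IVE done at home: the home is correct.
   - IVE at a store, mall or park: the home is wrong.

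5. **Does another route correct the third case?**
   - Contact by the principal investigator (Section 15.0): not tied to the home, but it sets no dispatch destination.
   - The participant's own call to staff or 911, urgent care and the emergency room (Section 15.0): also not tied to the home, but they depend on the participant acting.
   - Staff escort to a walk-in clinic or emergency room (Section 13.0, Follow-Up Phase): needs a staff member physically with the participant.
   - Geolocation on the clinician dashboard (Section 3.0, caption to Figure 2): gives a location, but no emergency text refers to it.

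6. **Could the answer lie elsewhere?** Section 13.0 refers twice to a Human Subjects section, once for risks and once for the handling of clinical deterioration. The headings of Section 15.0 match the risk topics listed there, so Section 15.0 is probably the section meant. If it is a separate document, it was not available to check.

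Result: in the supplied text, the only written dispatch destination is wrong for an IVE held away from home, and nothing corrects it.

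**The case against.** The strongest reply is that the sentence is silent on IVEs and not wrong about them. Read after the telephone steps that precede it, home dispatch is a sensible welfare check. That is a fair account of how the sentence came about. But the rule is written for any staff member and any doubt about safety, in a block that expressly includes treatment. A coach looking for the emergency instruction would find this one.

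The second reply is practical, and most of it stands. In a coached IVE the coach can see and hear the participant, has geolocation on the dashboard and knows the agreed site. A sensible responder would ask for the location. Section 2.0 describes the exposure targets as objectively safe, and Section 5.0 excludes people at immediate suicidal or homicidal risk. These facts make a misdirected response unlikely, but they do not make the written destination correct.

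The third reply is the team's statement in Section 15.0 that these methods resolved every participation-related problem in its earlier trials. This is reassuring about the methods in general. But Section 2.0 says that IVEs are usually invisible to the provider and that this system is the first to target them in the patient's real-world setting. The earlier record therefore says little about a crisis seen live away from home.

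Two stronger readings are tempting, and the documents support neither. A reader might infer that responders would in fact go to the wrong place, or that the number of coached IVEs measures the danger. The text shows only a faulty instruction. Ordinary exposures are not emergencies, and neither the emergency rate nor the share of IVEs done at home is stated. A reader might also infer that naming one county's crisis unit leaves participants elsewhere uncovered. EMS is the stated alternative, and the documents do not say how many participants live or do exposures outside that county.

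**Conclusion.** The point holds as a minor defect in a safety procedure. Followed literally, the dispatch rule gives the wrong destination when staff learn of a crisis during an IVE away from home, and no other part of the supplied text names the right one. The practical risk is small and cannot be put into numbers from the documents.

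The conclusion rests on two assumptions: that the rule applies to treatment contacts, which its wording supports although its heading and the steps before it point to a narrower use, and that no separate Human Subjects document already covers IVEs. For these reasons confidence is moderate.

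**What to change.** In Section 15.0, replace the home as the destination with: *the participant's current location (home, agreed IVE site, or dashboard geolocation), served by the crisis or EMS service for that location*. When to dispatch remains the investigators' clinical decision.

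So that the location is at hand, add two short steps:

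- **Coached IVEs.** Section 10.0 already has a step in which the coach "will provide a brief (3 min) review of the instructions before the patient begins the IVE". The coach confirms the site and a call-back number then. Section 10.0 allows an IVE to go ahead without wifi, so a noted site is a useful backup to geolocation.
- **IVEs set as homework, in both arms.** The therapist notes the planned site when the homework is set. This uses no live data, so the contrast between guided and record-only exposure is unchanged.

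If a separate Human Subjects document already gives an IVE destination, a cross-reference in Section 15.0 is enough.

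The cost is one changed phrase and, at an assumed minute each, one note per IVE or homework plan. It applies to every coached start and not only to the minimum of three accompanied IVEs, because Section 10.0 has the coach open later sessions as well. The notes are location data and need the same secure storage as the IVE records. No device, endpoint or analysis changes.
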